# SAMPLE SIZE CALCULATION

If there is a true difference in favour of the experimental treatment of 5%, then 236 patients (118 per treatment arm) will be required to be 90% sure that the upper limit of a one-sided 95% confidence interval (or equivalently a 90% two-sided confidence interval) will exclude a difference in favour of the standard group of more than 5%.

# DATA ANALYSIS PLAN

Per-protocol pre-specified analyses will include study participants with complete delivery data available to compare primary and secondary outcomes by treatment arms. Two-sample comparisons for normally-distributed variables will be performed using the Student's *t*-test, for non-normally distributed variables by Mann Whitney U-test, and for proportions by Fisher's exact test. Safety and tolerability to determine the rate of adverse events will be assessed from the incidence of symptoms/signs during the in-patient period until discharge and at 4 weeks post-discharge using Poisson regression. Unless otherwise stated, all *P*-values will be two-tailed with 0.05 taken as significant.

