#### **Hypothesis**

Misoprostol has the potential to cause dose dependent adverse effects such as uterine hyperstimulation and rupture that may lead to adverse and/or severe adverse labour outcomes. Therefore, the ideal oral misoprostol IOL regimen should be one that utilises a low dose. In the present study, we hypothesis that a regimen commencing with a lower dose of oral misoprostol administered at 12mcg per dose and

gradually increased to a maximum of 50mcg per dose over 24 hours will have a non-inferior efficacy and safety profile in inducing labour compared to a regimen that is administered at 25mcg per dose at baseline and gradually increased to a maximum of 50mcg per dose within 24 hours.

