#### **Study design**

The present study will be an open-label randomized controlled trial. Based on computergenerated block randomization, eligible patients will be allocated 1:1 to the standard treatment group (see Figure 1) or to the low dose oral misoprostol group (Figure 2). Allocated treatments will be concealed in sealed numbered envelopes which will be opened in sequence by study medical or nursing staff and the specified treatment administered.

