#### **ETHICAL ISSUES**

We have experience in conducting research in this setting [10-12] and do not anticipate that we will be encountering serious ethical issues during the conduct of this study. However, some ethical issues that we may confront include:

- Age of consent: Because teenage pregnancy is common in our setting, we will ensure only women over the age of 18 are eligible for inclusion in this study.
- Written Informed Consent Procedures: Women who fulfil the selection criteria for induction of labour and are eligible and willing to participate in the trial will be asked to complete formal written informed consent procedures that will include face-to-face discussion with the investigator or designated staff member of the clinical trial team who will then explain key study objectives, procedures, potential risks and benefits in more

detail. This will include a clear explanation that participation in this trial is entirely voluntary, and that withdrawal is possible at any time without having to give a reason.

- **Patients' autonomy**: We are aware of the challenges involved when clinical research is integrated with patient care in resource-limited settings such as ours [13]. However, the study protocol will be adhered to at all times and no deviation to the study protocol will be entertained without proper ethical approval.
- **Patient confidentiality**: Each study participant will be assigned a study code and we will separate the patients name from the information and samples collected. We will be very careful about the information that we collect, ensuring this information is made available only to the doctors or nurses providing patient-care.

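### A per-protocol set that is undefined and limited to complete delivery data is the only stated efficacy analysis in an open-label non-inferiority trial, so exclusions after randomisation could bias the result in either direction

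*Protocol*

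**What the plan says.** Under Data Analysis Plan, the protocol gives one set for efficacy: "Per-protocol pre-specified analyses will include study participants with complete delivery data available to compare primary and secondary outcomes by treatment arms". The only criterion it attaches is availability of delivery data. It does not say which departures from protocol remove a woman from the set. No all-randomised efficacy analysis is named in any section. The intention-to-treat wording under the two treatment arms describes going on to Foley catheterisation after a second cycle without progress, and does not name an analysis set.

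The setting for that choice is as follows.

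- Study design: "The present study will be an open-label randomized controlled trial", with 1:1 allocation.
- Hypothesis: the low-dose regimen "will have a non-inferior efficacy and safety profile in inducing labour compared to a regimen" starting at the higher dose.
- Sample Size Calculation: the trial must give a confidence limit that "will exclude a difference in favour of the standard group of more than 5" percentage points. It uses the "upper limit of a one-sided 95% confidence interval (or equivalently a 90% two-sided confidence interval").
- Ethical Issues: "withdrawal is possible at any time without having to give a reason".

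**The concern.** A per-protocol analysis is a legitimate part of a non-inferiority trial. The weakness is that here it stands alone, is not defined, and is narrowed further to women with complete delivery data. Once women can leave the analysis after randomisation, the two arms are no longer guaranteed to be comparable.

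The protocol's own features make exclusions related to outcome plausible. Staff know the allocation. The arms follow different dose schedules, totalling 500 and 348 mcg in the first 24 hours. A full course with its rest period can last 24 + 24 + 16 = 64 hours, during which a woman may withdraw. Whether she stays could therefore depend on her arm and on how her induction is progressing.

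The stake is the trial's central conclusion. A margin of 5 points on 118 women per arm is about 6 women (0.05 × 118 = 5.9), so losing a handful of failures selectively can matter. With no as-randomised analysis beside it, the reader could not see whether that had happened.

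**Working it through.** **Inputs from the protocol.** Margin 5 points, one-sided 5% error, 90% power, 118 per arm, and an assumed true advantage of 5 points for the experimental arm ("If there is a true difference in favour of the experimental treatment of 5" points). The standard-arm success rate is not stated.

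**Step 1: reproduce the sample size.** n per arm = (z₀.₉₅ + z₀.₉₀)² × [p_S(1 − p_S) + p_L(1 − p_L)] / (true difference + margin)².

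With p_S = 0.90 and p_L = 0.95: (1.645 + 1.282)² × (0.09 + 0.0475) / 0.10² = 117.8, so 118 per arm and 236 in total. Standard rates of 0.89 and 0.91 give 133 and 104 per arm. A 90% standard rate is therefore the value that fits, and I use it below as an inferred assumption.

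**Step 2: false non-inferiority rate when true success sits on the margin.** Take p_S = 0.90 and p_L = 0.85. Suppose failures equal to a fraction f of an arm's women are missing from the analysed set. That arm's observed success becomes p/(1 − f) on 118(1 − f) women. Then

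P(claim) = Φ[(d + 0.05)/SE − 1.645],

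where d is the analysed low-dose minus standard difference and SE = √[p_S(1 − p_S)/n_S + p_L(1 − p_L)/n_L], using the analysed values.

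Example, f = 0.03 in the low-dose arm only: p_L = 0.85/0.97 = 0.8763 on 114.5 women; d = −0.0237; SE = 0.0414; (0.0263/0.0414) − 1.645 = −1.009; Φ = 0.156.

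| What is missing from the analysed set (assumed) | Observed standard / low dose | False non-inferiority |
|---|---|---|
| Nothing, or losses unrelated to outcome | 90.0% / 85.0% | 5.0% |
| Standard arm only, failures = 3% of women | 92.8% / 85.0% | 1.0% |
| Both arms, failures = 3% of women in each | 92.8% / 87.6% | 4.6% |
| Both arms, failures = 5% of women in each | 94.7% / 89.5% | 4.3% |
| Both arms, 10% of failures in each | 90.9% / 86.3% | 6.0% |
| Both arms, 20% of failures in each | 91.8% / 87.6% | 7.4% |
| Both arms, one third of failures in each | 93.1% / 89.5% | 10.0% |
| Low-dose arm only, failures = 2% of women | 90.0% / 86.7% | 10.9% |
| Low-dose arm only, failures = 3% of women | 90.0% / 87.6% | 15.6% |
| Low-dose arm only, failures = 5% of women | 90.0% / 89.5% | 29.9% |

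For scale, 3% of 118 is about 4 women. In the low-dose arm that is 3/15 = 20% of all failures, and 5% is 5/15 = one third of them.

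**Step 3: check by simulation.** In 400,000 runs with a one-sided 95% Wald limit, the rate was 5.2% with nobody excluded. It was 9.6%, 16.5% and 26.7% with 10%, 20% and 30% of low-dose failures left out, and 6.5%, 8.0% and 10.1% with the same shares left out of both arms. The approximation is adequate.

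**Step 4: power, a secondary matter.** The total of 236 includes no allowance for exclusions. At 90% against 95%, outcome-unrelated exclusions of 10% (106 per arm) or 20% (94 per arm) lower power from 90% to 87.1% or 83.4%.

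**The case against.** The case for the plan has substance.

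- **Typical failures stay in.** Caesarean section after failed induction is a component of the primary endpoint, so such a woman has delivery data and counts as a failure. Second courses, Foley catheterisation and oxytocin are steps the protocol itself provides, so they are not departures from it. This limits how many failures would go missing, but it does not deal with women who withdraw or whose outcome is not recorded.
- **The protocol promises adherence throughout.** That is a stated intention, and it sits beside a guaranteed right to withdraw. If exclusions turned out to be nil, the as-randomised analysis would simply match the per-protocol one.
- **A statistical analysis plan may add another set.** That is possible. The protocol has nevertheless made a choice here and named one set for the primary and secondary comparisons, so the choice can be judged as it stands.
- **The large error rates are one-sided worst cases.** This is right. The 16% and 30% figures require failures to be lost from the low-dose arm alone. Other patterns leave the error near or below 5%.

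A reader might go further and infer that women who refuse doses, deviate or transfer will be dropped. The protocol does not say so: per-protocol is undefined and transfer is not mentioned. A reader might also take the low-dose arm to be the slower one and expect bias in its favour. The protocol does not say this either, and its sample size assumes that arm does better by 5 points. Nor is the safety analysis expressly confined to the per-protocol set.

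**Conclusion.** The point stands in this form: the only efficacy set the protocol names is undefined, depends on events after randomisation, and has no all-randomised analysis beside it. In an open-label non-inferiority trial with free withdrawal, this leaves the main conclusion open to bias of unknown direction.

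The false non-inferiority rate, nominally 5%, ranges from about 1% to about 30% over the patterns examined. The range rests on an inferred 90% standard rate, a true low-dose rate of 85%, and assumed exclusion fractions. The protocol gives none of these. The documents do not support saying that the plan will produce a false claim of non-inferiority, only that it could and that nothing in the plan would reveal it. The figure of 236 is not shown to be wrong, and the power loss depends entirely on exclusion rates that are assumed.

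**What to change.** 1. Analyse all randomised women by allocated arm as one of two required sets. Collect mode of delivery, neonatal admission and maternal and perinatal deaths even when dosing stops. For women who withdraw from the trial, do this only as far as consent allows, and add consent and ethics wording to cover it.
2. Define the per-protocol set before the data are examined by arm, listing the departures that remove a woman, and keep it as the second set.
3. Claim non-inferiority only if both sets exclude the 5-point margin.
4. State how delivery outcomes that stay missing are handled, for example counted as failures with a sensitivity analysis under other assumptions. Report exclusions and missing outcomes by arm, with reasons.

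The cost is revised analysis wording, a consent clause and some extra outcome collection. The small downside is that both sets must agree before the claim can be made. No treatment procedure changes. If the sponsor expects exclusions, the sample size could allow for them: keeping 118 evaluable per arm needs 132 randomised per arm at 10% exclusions (118/0.90 = 131.1) or 148 at 20% (118/0.80 = 147.5).

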# **Primary endpoint**

The primary outcome measured would be the proportion of women who have a successful live vaginal delivery without any severe adverse event including: i) failed induction necessitating cesarean section, ii) maternal death, iii) retained placenta, iv) perinatal death, and/or v) neonatal admission to special care nursery.

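### The analysis plan compares the primary proportion by a two-tailed Fisher's exact test, which uses neither the 5-point margin nor the confidence limit on which the non-inferiority trial was sized

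*Protocol*

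**What the plan says.** Four places in the protocol bear on the primary comparison.

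- **Hypothesis.** The low-dose regimen "will have a non-inferior efficacy and safety profile in inducing labour" compared with the standard regimen.
- **Primary endpoint.** It is binary: "the proportion of women who have a successful live vaginal delivery without any severe adverse event".
- **Sample Size Calculation.** With a true 5% advantage for low dose, 118 women per arm give 90% assurance that "the upper limit of a one-sided 95% confidence interval (or equivalently a 90% two-sided confidence interval) will exclude a difference" of more than 5% in favour of the standard group. This fixes a margin, a direction and a one-sided 5% error level.
- **Data Analysis Plan.** The listed tests are to be used for both primary and secondary outcomes: the t-test or Mann-Whitney test for continuous variables, and "for proportions by Fisher's exact test". Unless an exception is stated, P-values "will be two-tailed with 0.05 taken as significant".

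The Data Analysis Plan does not mention the margin, a confidence interval for the difference, a one-sided criterion or non-inferiority. It makes no exception for the primary endpoint.

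**The concern.** The two sections answer different questions. Write d for the true success proportion on low dose minus that on standard.

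- The Hypothesis and Sample Size Calculation set the null hypothesis d ≤ -5 points, to be rejected when a confidence limit excludes that deficit.
- Fisher's two-tailed test has the null hypothesis d = 0. Its P-value does not depend on the margin.

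An analyst who follows the Data Analysis Plan alone obtains a P-value for equality and never computes the interval that justified the sample size. A non-significant P-value would then leave the trial's main question unanswered, whether or not the data in fact exclude a 5-point deficit. The two rules can also point in different directions on the same data, so it matters which one is fixed before the results are seen.

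**Working it through.** **Inputs.** From the protocol: 118 per arm, 1:1 allocation, margin 5 points, assumed true benefit +5 points, one-sided 5% level and 90% power for sizing; Fisher's test, two-tailed 0.05, for analysis. The success rate in the standard arm is not given. It is taken as 90%, with 80% and 70% shown as a range.

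**Step 1: reproduce the sample size.** With p_S and p_L the success proportions on standard and low dose,

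n per arm = (z_0.95 + z_0.90)² × [p_S(1 - p_S) + p_L(1 - p_L)] / (benefit + margin)²

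At p_S = 0.90 and p_L = 0.95: (1.645 + 1.282)² × (0.0900 + 0.0475) / 0.10² = 117.75, rounded up to 118 per arm, 236 in total. This matches. Standard-arm rates of 89% and 91% give 133 and 104, and a one-sided 2.5% level at 90% against 95% gives 145. The stated figure is therefore a non-inferiority calculation at one-sided 5%, and 90% is the rate on the grid tried that returns it.

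**Step 2: compare the two rules at 118 per arm.** All outcome tables were enumerated with exact binomial probabilities.

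- Fisher rule: two-tailed P < 0.05.
- Sizing rule: (p_S - p_L) + 1.645 × SE < 0.05, using observed proportions, with SE = √[p_S(1 - p_S)/118 + p_L(1 - p_L)/118].

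| Assumed standard rate | True +5: Fisher significant | True +5: sizing rule met | True -5: Fisher non-significant | True -5: sizing rule met |
|---|---|---|---|---|
| 90% | 22% | 91% | 84% | about 5% |
| 80% | 13% | 65% | 88% | about 5% |
| 70% | 11% | 53% | 90% | about 5% |

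At 90% against 95%, 69% of trials meet the sizing rule while Fisher is non-significant. With low dose truly 10 points worse (90% against 80%), Fisher is still non-significant in 49% of trials, while the sizing rule is met in 0.3%.

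**Step 3: two single results, standard against low dose.**

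- 106/118 against 98/118: Fisher P = 0.18. Difference = -8/118 = -6.8 points; SE = √(0.898 × 0.102/118 + 0.831 × 0.169/118) = 0.044; 90% interval -14.1 to +0.5 points. Non-inferiority is not shown.
- 106/118 against 112/118: Fisher P = 0.22. Difference = +6/118 = +5.1 points; lower 90% limit -0.6 points. Non-inferiority is shown.

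Both P-values are non-significant and similar in size, yet the answers to the trial's question are opposite.

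**The case against.** The strongest defence is that the protocol does contain the right criterion. The Sample Size Calculation gives the margin, the direction and the limit. The two-tailed rule in the Data Analysis Plan is only a default that yields to exceptions stated elsewhere. That plan is a generic list of tests by variable type, and a separate statistical analysis plan may hold the decision rule. Part of this stands: the criterion exists and only has to be carried over. It does not remove the conflict. The sizing section says what the sample size should achieve, not how the data will be analysed, whereas the Data Analysis Plan explicitly covers the primary outcome and names a test for proportions. This is a contradiction in what the protocol fixes, not a detail left for later.

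Three stronger readings are tempting but not supported.

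- *That the planned test can never support the claim.* A Fisher result significant in favour of low dose would imply non-inferiority; no table at 118 per arm with such a result fails the sizing rule. Under 90% against 95%, that route is open in about 22% of trials.
- *That the investigators will treat P > 0.05 as non-inferiority.* The protocol nowhere says so. The 84% to 90% pass rates show what that reading would cost; they are not the error rate of a planned rule.
- *That the contrast of 22% with 90% holds generally.* It belongs to one assumed standard-arm rate. At lower rates the sizing rule itself loses power, to 65% and 53%.

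Nor is the difference between one-sided 5% and two-sided 5% an error in itself. A confidence limit for one question and a default P-value level for others can coexist.

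**Conclusion.** The point holds as an inconsistency within the protocol. The hypothesis and sample size pose a non-inferiority question with a 5-point margin, and the analysis named for the primary proportion is a test of equality that uses neither that margin nor the planned limit. This mismatch is read from the text and depends on no assumed rate.

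Its size does depend on the unstated standard-arm rate. Over assumed rates of 90% down to 70%, with a true 5-point benefit, Fisher's test is significant in 22% down to 11% of trials, against 91% down to 53% for the sizing rule. The agreement with the stated 90% power at the top of that range rests on the 90% assumption. It should be corrected before analysis, because it decides what the trial can conclude.

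**What to change.** Add to the Data Analysis Plan:

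> The primary analysis is the difference in success proportions (low dose minus standard) with a two-sided 90% Miettinen-Nurminen confidence interval. Non-inferiority is concluded only if the lower limit is above -5 percentage points.

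Keep Fisher's exact test, two-tailed at 0.05, for secondary or supportive comparisons, and say that a non-significant result from it is not evidence of non-inferiority. It would also help to state the standard-arm success rate behind the 236, so that readers can check the calculation.

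The cost is a few sentences of protocol text. Design, data collection and the number of women are unchanged. The working above uses the simple Wald limit because it matches the sizing formula. The Miettinen-Nurminen interval is proposed so that one method is fixed in advance, and in the same enumeration it behaves very similarly.

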#### **ETHICAL ISSUES**

We have experience in conducting research in this setting [10-12] and do not anticipate that we will be encountering serious ethical issues during the conduct of this study. However, some ethical issues that we may confront include:

- Age of consent: Because teenage pregnancy is common in our setting, we will ensure only women over the age of 18 are eligible for inclusion in this study.
- Written Informed Consent Procedures: Women who fulfil the selection criteria for induction of labour and are eligible and willing to participate in the trial will be asked to complete formal written informed consent procedures that will include face-to-face discussion with the investigator or designated staff member of the clinical trial team who will then explain key study objectives, procedures, potential risks and benefits in more

detail. This will include a clear explanation that participation in this trial is entirely voluntary, and that withdrawal is possible at any time without having to give a reason.

- **Patients' autonomy**: We are aware of the challenges involved when clinical research is integrated with patient care in resource-limited settings such as ours [13]. However, the study protocol will be adhered to at all times and no deviation to the study protocol will be entertained without proper ethical approval.
- **Patient confidentiality**: Each study participant will be assigned a study code and we will separate the patients name from the information and samples collected. We will be very careful about the information that we collect, ensuring this information is made available only to the doctors or nurses providing patient-care.

## **CANDIDATURE TIMELINE**

The time as proposed by the University of Papua New Guinea By Law No:37 governing the Degree of Doctor of Medicine-Part 2 states that candidates admitting to the degree by presentation of a thesis would be required to complete 3-5 years. Therefore, I would like to complete my MD within 3 years.

During the 3 years of this MD program (2016-2018), I will spend most of the time continuing in my capacity to do clinical work and conduct these studies as part of continued professional education and research. I will spend some time to supervise, coordinate and train the staff about the study protocol and methods on a daily basis.

I hope to complete the proposed study by 2017 and to perform data analysis and write up in 2018. My detailed candidature timeline is proposed below:

## 2016

- January Submit Draft Research Proposal
- **February** Literature Review
- February Submit corrected draft Research Proposal to supervisors
- March Enrol for MD Program and submit Final Research Proposal
- March-April Submit for Ethical Approval from MHEC, MRAC, UPNG SMHS Ethics
  committee and register the trial
- April Commence data collection
- June Start Preliminary data entry and continue literature review
- August Continue research and data entry
- September Perform interim analysis on the first 30 participants (each arm)
- October Continue literature research and start writing background of thesis
- November Start writing methodology of the thesis
- **December** -Start writing 2016 annual report

- February Submit 2016 annual report to UPNG, SMHS post graduate office
- March Continue writing thesis background and methodology
- May Aim to have recruit 80 participants in each arm and to perform the second interim analysis
- June Continue writing methodology of thesis and data entry
- November Required number for the study (236 in total) to be completed

• **December** Start writing 2017 Annual Report

